10.1 Preoperative phase

During the ~~first visit~~-selection phase, the principal investigator records patient data and checks eligibility criteria (inclusion and non-inclusion criteria).

Then, the data collected are:

Sociodemographic data:

- Age, sex, weight, height,

Medical history:

- Primary diagnosis and operative indication.
- Co-morbidities and risk factors: alcoholism, Overweight, anticoagulant intake, cardiovascular, Sagitta EVL-R tension, diabetes, thromboembolic history, Rheumatoid arthritis, Osteoporosis, Musculoskeletal comorbidity, other (to be defined)

Daily physical activity: these parameters is graded as:

- Bedridden
- Sedentary
- Semi sedentary
- Light activity
- Moderate activity
- Heavy activity

Classification of Charnley – Adversely impacting outcomes factors: this classification is graded as 3 levels (A: none factor, B: damage of the contralateral hip, C).

10.2 Operative phase

The investigator noted in the CRF all of the following items:

- Type of anesthesia
- Surgical approach
- Sagitta EVL-R device description and the overall assembly for the THA
- Perioperative complications such as surgical complications: all data will be recorded if concerning the treatment of the pathology.

10.3 Immediate postoperative phase

Radiological evaluation:

The inclination of the cup, the localization of the center of rotation, and the presence or not of a periprosthetic radiolucent lines will be followed and their potential locations. Moreover, the distance, the height of the stem comparing with an anatomic locator (greater or lesser trochanter) and the presence or not of a periprosthetic radiolucent line all around and its location.

10.4 Postoperative phases at 6 months, 1, 2, 5 to 8 years

Daily physical activity: this parameter is graded as:

- Bedridden
- Sedentary
- Semi sedentary
- Light activity
- Moderate activity
- Heavy activity

Classification of Charnley – Adversely impacting outcomes factors: this classification is graded as 3 levels (A: none factor, B: damage of the contralateral hip, C: Other associated morbidities interfering on the walking ability).

The global results of the surgery - through the global satisfaction of patients, the potential improvement of the walking ability, the functional improvement and the pain release; using closed-questions.

| | | | |
|--|------------------------------|---|-------------------------|
|  serf | Document No. | SAGITTA EVL-R STEMS – NOVAE / SAGITTA EVL-R CUPS | ID RCB : 2019-A01777-50 |
| | 2019-10-EVLR-N Version 02 | | |

Radiological evaluation:

The inclination of the cup, the localization of the center of rotation, and the presence or not of a periprosthetic radiolucent lines will be followed and their potential locations. Moreover, the distance, the height of the stem comparing with an anatomic locator (greater or lesser trochanter) and the presence or not of a periprosthetic radiolucent line all around and its location. Qualitative migration and subsidence of the implant are also deduced indirectly.

Postoperative Complications

Complications will be recorded as soon as there will be encountered in patients' files. All data will be recorded if available? Analysis of these events will be analyzed jointly with the investigator. In retrospective manner, No relevant events in nature or incidences will be declared following the procedure in the following section, if applicable. The investigator should investigate the occurrence of adverse events.

10.5 Postoperative phases at 5 to 8 years – Patient' phone call

Functional improvement: The assessment of the results of the hip surgery at the last follow-up will be evaluated postoperatively through the validated Oxford Hip Score. It will be monitored by a dedicated clinical research associate and the questionnaire will be fill in directly by phone with the patient.

11 Safety assessment

11.1 Adverse Device Effect (ADE)

Adverse event related to the use of an investigational medical device (Guidelines on medical devices ; Clinical investigations: serious adverse event reporting under Directives 90/385/EEC and 93/42/EEC , December 2010). This includes any adverse event resulting from insufficiencies or inadequacies in the instructions for use, the deployment, the implantation, the installation, the operation, or any malfunction of the investigational medical device.

This includes any event that is a result of a use error or intentional misuse.

11.2 Adverse events

During the study data harvest, safety assessments will consist of collecting retrospectively all adverse events and serious adverse events. The available Information about all adverse events in patients' files will be collected and recorded and followed as appropriate; principally during the phone call with simple questions.

An adverse event is the appearance or worsening of any undesirable sign, symptom, or clinical condition occurring during or after the surgery even if the event is not considered to be related to study device. Medical conditions/diseases present before starting study are only considered adverse events if they worsen after medical device implantation. Once an adverse event is detected in the patient file, it should be followed historically through the file until its resolution and assessment should be made through any change in severity, the suspected relationship to the medical device, the interventions required to treat it, and the outcome.

Any untoward medical occurrence, unintended disease or injury or any untoward clinical signs (including an abnormal laboratory finding) in subjects, users or other persons whether or not related to the investigational medical device (Guidelines on medical devices ; Clinical investigations: serious adverse event reporting under Directives 90/385/EEC and 93/42/EEC , December 2010).

This includes events related to the investigational device.

This includes events related to the procedures involved. For users or other persons this is restricted to events related to the investigational medical device.

11.3 Serious Adverse Events

A serious adverse event is an undesirable sign, symptom or medical condition which:

- is fatal or life-threatening
- results in persistent or significant disability/incapacity
- constitutes a congenital anomaly/birth defect

| | | |
|---|---|---------------------------------------|
|  Document No. 2019-10-EVLR-N | SAGITTA EVL-R STEMS – NOVAE / SAGITTA EVL-R CUPS | ID RCB : 2019-A01777-50 |
| | Version 02 | Page No. Page 22 sur 28 |

- requires inpatient hospitalization or prolongation of existing hospitalization
- is medically significant, i.e., defined as an event that jeopardizes the patient or may require medical or surgical intervention to prevent one of the outcomes listed above
 - This includes device deficiencies that might have led to a serious adverse event if a) suitable action had not been taken or b) intervention had not been made or c) if circumstances had been less fortunate.
 - A planned hospitalization for pre-existing condition without a serious deterioration in health, is not considered to be a serious adverse event.

The investigator must assess and record the relationship of each SAE with sagitta EVL-R stems, complete the information in the CRF, and inform by the usual way of reporting the sponsor (SERF).

12 Data flow

12.1 Case Report Forms - database

All protocol-required data should be recorded in an excel database (Microsoft office) while they are collected. The access to this database will concerned only the investigator and the sent clinical research associate of SERF. This recorded raw data will be transferred in SERF facilities and a copy of these raw data will be kept in the archives of the hospital. The duration of archiving is 15 years since the end of the study.

12.2 Source documents

Source documents include all recorded observations or notes of clinical activities and all reports and records necessary for the evaluation and reconstruction of the clinical research study. They include, but are not limited to subject file notes, imagery pictures and any other medical reports performed in the current practice.

The investigator will allow study-related monitoring, audits and regulatory inspection, providing direct access to source data.

12.3 Personal data

Personal data will be harvested on site to have a working document between the name, the patient file and the internal code of the patient for the sponsor document. The codification for the sponsor will be the two first letter of the investigation site (e.g. CHP for “Centre Hospitalier Poitiers”) and the order number of the included patient in the study (e.g. for the first included patient, CHP001). No direct personal data will be recorded by the sponsor such as the name and surname, the birth date. All is made to reduce the risk as much as possible.

All personal data that the sponsor need are specific.

Other personal data that will be recorded, analyzed and that the sponsor need:

- the intervention date,
- the type of intervention,
- the sex and
- the medical history.

No personal data that the sponsor needs will be transferred into another country or another organization. Processing of personal data is necessary for scientific research purposes.

All other requirements suggested by the General Data Protection Regulation (GDPR) are respected. No data protection officer was designated in SERF due to the low number of employees.

13 Data MANAGEMENT and Statistical data analysis

13.1 Data management

If missing, illegible or inconsistent data is detected, requests for additional information will be sent to the concerned investigator.

The consistency and validity of the database will be ensured by the clinical affairs project manager of SERF. Upon detection of errors or inconsistencies, additional information requests are sent to the investigator concerned; modifications will be incorporated into the database by the responsible person.

The database is then locked and statistical analysis can begin.

| | | | |
|---|----------------|---|-------------------------|
|  | Document No. | SAGITTA EVL-R STEMS – NOVAE / SAGITTA EVL-R CUPS | ID RCB : 2019-A01777-50 |
| | 2019-10-EVLR-N | | |

Version 02

Page No. Page 23 sur 28

13.2 Statistical analysis

The data will be analyzed using an excel Microsoft office 2016. All data will be expressed qualitatively and/or quantitatively (frequency and/or percentage). All data will finally be compared to those found in the bibliography.

The previous section includes the main elements of the statistical analysis plan. This plan may be revised to reflect any modifications to the protocol. Any such revisions will be made before freezing the database.

Statistical analysis will be performed in SERF's facilities.

14 Quality assurance

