
| | | |
|---|---|--------------------------------------|
|  Document No. 2019-10-EVLR-N | SAGITTA EVL-R STEMS – NOVAE / SAGITTA EVL-R CUPS | ID RCB : 2019-A01777-50 |
| | Version 02 | Page No. Page 6 sur 28 |

| | |
|-------------------------|---|
| | 
complication rate will be evaluated. Other specific complication rate would be evaluated if considered representative and pertinent.
 
The global satisfaction of patients will be measured at the last postoperative timepoints.
 
The walking ability will be measured at the last postoperative timepoints.
 
The global functional improvement will be measured at the last postoperative timepoints.
 
The pain release will be estimated at the last postoperative timepoints.
 
The length of the operated limb will be harvested to see of the chosen assembly was adequate and to see its evolution over time.
 
Secondary endpoints:
 
The endpoints are:
 
Postoperative Radiological assessments will be followed at immediate postoperative period and at 6 months, 1, 2, 5, and potentially between 5 to 8 years postoperatively. The inclination of the cup, the localization of the center of rotation, and the presence or not of a periprosthetic radiolucent line will be followed and its location. Moreover, the distance, the height of the stem comparing with an anatomic locator (greater or lesser trochanter) and the presence or not of a periprosthetic radiolucent line all around and its location.
 
The daily physical activity will be appreciated postoperatively at the last follow-up postoperatively.
 
The co-morbidity will be measured preoperatively and postoperatively at 6 months, 1, 2, 5, and potentially between 5 to 8 years postoperatively.
 
The global satisfaction of patients will be measured at the last follow-up between 5 and 8 postoperative years.
 
The walking ability will be measured at the last follow-up between 5 and 8 years postoperative years.
 
The global functional improvement will be measured at the last follow-up between 5 and 8 years postoperatively.
 
The pain release will be estimated at the last follow-up between 5 and 8 years postoperatively.
 
The length of the operated limb will be harvested at 6 months, 1, 2, 5 and/or at 5 to 8 years postoperatively, if available.
 
Adverse events all along the postoperative follow-up and if the information is available in patients files:
 
 • Nature and origins of complications. • graded as serious (leading to death, life-threatening condition, requiring hospitalization or lengthening of hospital stay, leading to permanent or significant disability); • or graded as not serious and as implant-related (migration, subsidence) or surgery-related (iatrogenic event) or other relationships (i.e. aseptic loosening...), idiopathic events, possible related pathology events, but not limited to. |

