| Study visits | 
There's no inclusion period because of the retro-prospective design of the study. Only a phone call will be performed following the start of the data collection. The data collection would be performed during 2 to 4 8 to 10 consecutive days, depending of the ease to consult patient files.
 
Duration of the follow-up period for each patient: until a maximum of 8 years postoperatively. In fact, operated patients between 2011 and 2014 in a single center will be potentially eligible. Therefore, the maximum follow-up through a phone call will be between 5 to 8 years.
 
Patients will be followed at 2 stages: through their medical files (pre-operative, per-operative, immediate post-operative and postoperative follow-up), and between 5 to 8 years after implantation through a single phone call.
 |
| Study population | 
Constitution and follow-up of a cohort of patients operated for a primary total hip arthroplasty or a revision of hemiarthroplasty or total hip arthroplasty with implantation of
 |

the sagitta EVL-R femoral stem at a minimum. Most of time, several implants of the assembly are changed in case of revision. In case of primary surgical intervention, a stem + head and intermediate cup will be implanted for hemiarthroplasty; and a stem + head + insert + cup will be implanted for a total hip arthroplasty.

Inclusion criteria:

- Patients over 18 years old.
- Patients that were treated with the sagitta EVL-R stem for an indication of arthroplasty and according to the Instruction For Use (IFU).
 - Primary or secondary arthrosis,
 - Advanced joint destruction resulting from rheumatoid arthritis or traumatic arthritis,
 - A fracture or an avascular necrosis,
 - Following a previous surgical operation, on condition that the new device does not interfere with the material in place.
 - indicated in the case of primary or secondary arthrosis, displaced sub-capital or transcervical fracture as well as stages I and IIB bone loss according to the PAPROWSKI classification.
 - The SAGITTA EVOLUTION for REVISION implant is recommended for indications according to the bone loss classifications of SOFCOT stages I to VI, PAPROSKY types I to VI and the AAOS types Ia to Ic.
 - Dysplasia
- Patient being informed to the study and non-opposed of its participation and the use its pertaining data.
- Patients with a minimum follow up of 24 months.

Non-inclusion criteria:

- Patient presenting a contraindication indicated in the IFU.

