- As well as the face femur picture, the profile view of the femur would inform (in another dimension) about a potential subsidence / or a radiolucent line confirming a radiological and/or a clinical loosening of stem, that can lead to a surgical revision.
- The face radiography of the cotyle will mainly measured the inclination of the implant and its stability over time through its migration. The radiolucent line will be appreciated (De LEE and Charnley scales) to emphasize of potential radiological level of loosening. This finding may have no clinical impact on the patient daily life. It will depend of the level of loosening of the cup and its evolution.

The daily physical activity will be harvested postoperatively to see the incidence of the reparation of the patient daily autonomy at their last timepoints.

The co-morbidity will be measured preoperatively and postoperatively using the Charnley classification. The goal is to estimate if the co-morbidity may be detrimental to the clinical results and their evolution and potentially to identify the nature of detrimental factors.

All complications will be recorded during the study. A global survival rate would therefore be calculated at each timepoints. As the same manner, an aseptic loosening rate and a global complication rate will be evaluated. Other specific complication rate would be evaluated is considered representative and pertinent.

The global satisfaction of patients will be measured at the last postoperative timepoints.

The walking ability will be measured at the last postoperative timepoints.

The global functional improvement will be measured at the last postoperative timepoints.

The pain release will be estimated at the last postoperative timepoints.

The length of the operated limb will be harvested to see if the chosen assembly was adequate and to see its evolution over time.

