8.2 Inclusion criteria

The inclusion and exclusion criteria are controlling legal aspects of a clinical study in general; and the respect of indications cited in the instruction for use of the medical device. There's no other imposed restrictions.

The inclusion criteria are:

- Patients over 18 years old.
- Patients that were treated for an indication of arthroplasty and according to the Instruction For Use (IFU).
 - Primary or secondary arthrosis,
 - Advanced joint destruction resulting from rheumatoid arthritis or traumatic arthritis,
 - A fracture or an avascular necrosis,
 - Following a previous surgical operation, on condition that the new device does not interfere with the material in place.
 - indicated in the case of primary or secondary arthrosis, displaced sub-capital or transcervical fracture as well as stages I and IIB bone loss according to the PAPROWSKI classification.
 - The SAGITTA EVOLUTION for REVISION implant is recommended for indications according to the bone loss classifications of SOFCOT stages I to VI, PAPROSKY types I to VI and the AAOS types Ia to Ic.
 - Dysplasia
- Patient being informed to the study and non-opposed of its participation and the use its pertaining data.
- Patients with a minimum follow up of 24 months.

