8.4 Definitive inclusion

A patient is definitely included in the study if declared eligible during the electronic file assessment.

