8.5 Exclusion criteria

After inclusion, patients can be excluded from the study if the final follow up is 24 months and if available data at the 24 months postoperative visit is too poor.

9 Study procedures

Patient information:

This observational study does not require any additional eligibility criteria, any additional exam. According to French regulation, each patient is appropriately informed of his/her freedom to decline or agree to participate to the study (thanks to the information note) and of his rights regarding medical data collection.

Study withdrawal:

Patients may withdraw from the study at any time at their own request, or they may be withdrawn at any time at the discretion of the investigator or sponsor for safety, behavioral, or administrative reasons. In any circumstance, every effort should be made to document patient outcome, if possible.

| | | | | | |
|--|----------------|---|-------------------------|----------------|--|
|  serf | Document No. | SAGITTA EVL-R STEMS – NOVAE / SAGITTA EVL-R CUPS | ID RCB : 2019-A01777-50 | | |
| | 2019-10-EVLR-N | | Page No. | Page 19 sur 28 | |

10 Collected data

Patients will be followed at 2 stages: in their medical history files and through a phone call [after](#) the surgery.

| Endpoints | Preoperative | Per-operative | Immediate post-operative | Visit 6 months | Visit 1 year | Visit 2 years | Last visit over 2 years | Phone call to patients |
|--|---|---------------|--------------------------|----------------|--------------|---------------|-------------------------|------------------------|
| Patient information (gender, age, weight, height) | X | | | | | | | |
| Eligibility criteria | X | | | | | | | |
| Medical & surgical history | X | | | | | | | |
| Oxford questionnaires | | | | | | | | X |
| Daily physical activity | | | | | | | | X |
| Charnley Classification | X | | | X | X | X | X | X |
| Surgery - Assembly components description | | X | | | | | | |
| Peroperative Incidents | | X | | | | | | |
| Global results: Patient satisfaction Walking ability Functional improvement Pain release | | | | | | | | X |
| Length of the operated limb | | | | | | | | X |
| Radiologic assessment | Inclinaison of the Cup and localization of the center of rotation | | X | X | X | X | X | X |
| | Periprosthetic radiolucent line - Cup | | X | X | X | X | X | X |
| | Stem height/ anatomic locator | | X | X | X | X | X | X |
| | Periprosthetic radiolucent line - stem | | X | X | X | X | X | X |

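### Late implant survival, loosening and complication rates need a fixed-time estimate: as section 13.2 is written, a plain percentage at last contact would mix unequal follow-up lengths

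*Protocol*

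**What the plan says.** **Method.** Protocol section 13.2: "All data will be expressed qualitatively and/or quantitatively (frequency and/or percentage). All data will finally be compared to those found in the bibliography". The same section says that the main elements of the statistical analysis plan are already in the protocol, and it allows revision before the database is frozen.

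**What is promised.** Section 6.2, repeated in the section 1 summary: "A global survival rate would therefore be calculated at each timepoints". Aseptic loosening and global complication rates are to be evaluated in the same way.

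**Length of follow-up.**
- Section 8.2 requires "Patients with a minimum follow up of 24 months".
- Section 1 (Study visits) says that "the maximum follow-up through a phone call will be between 5 to 8 years".
- After the 2-year visit, Table 1 in section 10 has only "Last visit over 2 years" and the phone call. Section 10.4 goes from 2 years to one phase covering 5 to 8 years.

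**Who is analysed.**
- Section 8.4: "A patient is definitely included in the study if declared eligible during the electronic file assessment".
- Section 8.5: "patients can be excluded from the study if the final follow up is 24 months" and the 24-month data are too poor.
- Section 15.1 instead has the patient agree orally, during the call, to be included.

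**The concern.** A percentage with a single denominator is sound when every patient has been observed for the same time. Up to 2 years that holds for the included patients, because 24 months is the minimum. Beyond 2 years it does not. One patient's last information may come from a file entry in year 3, another's from a call in year 5, another's from a call in year 8. The share with a revision at last contact then depends on the mix of follow-up lengths as well as on the implant.

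The denominator is also open. Under section 15.1 every included patient was reached by phone, so status at about 5 years should be known for all. Under sections 8.4 and 8.5 patients with file follow-up only may remain.

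Comparison with the literature is the only comparison planned, and section 16.1 says the results will serve mainly as evidence of performance and safety. The revision rates that the protocol itself cites, in section 3.1, are given at 1 and 5 years. A pooled percentage at 5 to 8 years has no counterpart among them.

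**Working it through.** The protocol gives no estimate, margin or power for these rates, and the sample size of 120 is stated to be arbitrary. There is no figure of the plan's own to reproduce. The calculation only sizes the effect.

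**Inputs from the protocol**
- Cited revision rates (section 3.1): total hip arthroplasty 2.4% at 1 year and 4.3% at 5 years; hemiarthroplasty 1.6% and 2.5%. The protocol does not name them as the comparator.
- N = 120 (section 8.1); minimum follow-up 24 months (section 8.2).
- Surgery 2011 to 2014 (section 1), study start and end of follow-up around November 2019 (section 7.3). A call in mid-November 2019 falls 4.9 to 8.9 years after surgery, slightly wider than the stated 5 to 8.

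**Assumptions (not in the protocol)**
- The hazard of years 1 to 5 continues to year 8.
- Last contact is spread evenly over 5 to 8 years.

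**Step 1: hazards (total hip arthroplasty)**
- Year 1: h1 = −ln(1 − 0.024) = 0.02429.
- Later years: h2 = (−ln(1 − 0.043) − h1)/4 = (0.04395 − 0.02429)/4 = 0.00491 per year.
- Cumulative risk for t ≥ 1: F(t) = 1 − exp(−h1 − h2(t − 1)).

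**Step 2: fixed-time risk against pooled percentage**

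| Illustration | F(5) | Mean of F over 5 to 8 years | F(8) |
|---|---|---|---|
| Total hip arthroplasty rates | 4.30% | 5.00% | 5.70% |
| Hemiarthroplasty rates | 2.50% | 2.84% | 3.17% |
| Assumed constant 1% per year | 4.9% | 6.3% | 7.7% |
| Assumed constant 3% per year | 13.9% | 17.7% | 21.3% |

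For total hip arthroplasty the gap to the 5-year rate is 120 × (0.0500 − 0.0430) = 0.84 patients. For hemiarthroplasty it is 0.40 patients. At 1% per year the gap is 1.4 points, and at 3% it is 3.8 points.

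**Step 3: dependence on the follow-up mix.** Let 10%, 25% or 50% of patients have last contact spread over 2 to 5 years. The pooled percentage under the total hip arthroplasty rates becomes 4.9%, 4.6% or 4.3%, with the implant's risk unchanged.

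**Step 4: denominator at 5 years.** Let a fraction p have file information only, ending evenly over 2 to 5 years. The mean of F over 2 to 5 years is 3.59%.
- A = known events by 5 years over all 120 = (1 − p)(4.30%) + p(3.59%).
- B = the same events over patients with known 5-year status = A/(A + (1 − p)(1 − 0.043)).

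| p (assumed) | A | B |
|---|---|---|
| 0 (all reached by phone) | 4.30% | 4.30% |
| 10% | 4.23% | 4.68% |
| 30% | 4.09% | 5.75% |

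**Step 5: behaviour of the alternative.** In 8,000 simulated cohorts of 120 with independent censoring, the mean Kaplan-Meier estimate at 5 years is 4.3% for each p in step 4, with a standard deviation of 1.8 to 1.9 points.

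**Step 6: sampling error.** The exact 95% interval for 6/120 (5.0%) is 1.9% to 10.6%, wider than the gaps under either set of cited rates.

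**The case against.** **Section 13.2 says how data are expressed, not how survival is estimated.** A Kaplan-Meier estimate is also reported as a percentage, and the term survival rate does not exclude it. A reader might infer that the protocol rules out a time-to-event analysis. It does not. What stands is that section 13.2 gives one form for all data, says that the main elements of the plan are already in the protocol, and attaches no late rate to a fixed time.

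**The late rates do not rest on the phone call alone.** Sections 10.4 and 11.2 take complications from the patient files as they are found there, and section 12.3 records the intervention date. A reader might infer that these rates cannot be matched to published ones at all. That holds only for a pooled crude percentage. Dated events in the files would allow a 5-year estimate.

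**The missing 5-year column in Table 1 is a separate matter.** The lists that name 5 years (for example "at 6 months, 1, 2, 5, and potentially between 5 to 8 years postoperatively") concern radiology, comorbidity and limb length. They do not schedule the survival or complication rates, so the mismatch with Table 1 is no evidence of a fault in those rates.

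**Event and death dates may already be collected.** The case report form (appendix 19.6) is not shown, so their absence cannot be asserted.

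**The effect is small, and the illustration is weak.** The gap is below one patient in 120 under the cited rates, and no test or acceptance threshold depends on it. The largest denominator effect needs an assumed 30% with file follow-up only, and a denominator that keeps those patients' events but drops those who were event-free. This stands. In addition, section 6 says the stem is used mainly for revision surgery, so the cited rates may not represent this cohort. The gap grows if the true hazard is higher.

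**Conclusion.** The point holds as an optional, cheap improvement. If section 13.2 is applied as written, the late percentage moves with the mix of follow-up lengths and with an undecided denominator, and it has no fixed-time counterpart in the literature.

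Under the cited arthroplasty rates the pooled figure exceeds the 5-year risk by 0.7 points (total hip) or 0.3 points (hemiarthroplasty), below the sampling error at N = 120. Under an assumed 1% per year it exceeds it by about 1.4 points. All these sizes rest on an assumed late hazard and an assumed spread of last contacts; the protocol gives neither. If every included patient was reached by phone, the two 5-year denominators agree and only the pooling issue remains.

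A reader might go further and infer that the study's safety conclusions, or its primary endpoint, are compromised. The documents do not support that. The rates are secondary, the primary endpoint is the Oxford Hip Score, percentages up to 2 years are sound for the included patients, and the files may hold what a fixed-time estimate needs.

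**What to change.** Before the database is frozen, as section 13.2 allows:

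1. State that implant survival and aseptic loosening are estimated by Kaplan-Meier, or by cumulative incidence with death as a competing event, at 1, 2 and 5 years, with numbers at risk and 95% confidence intervals.
2. Make sure that the single data harvest records dates of event, death and last contact, or the visit interval where a date is missing, if the case report form does not already do so.
3. Compare only with literature rates at the same time point.
4. Reconcile sections 8.4 and 8.5 with section 15.1, and state whether patients not reached by phone stay in the analysis.

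**Cost.** A few sentences, possibly a few extra columns, and some analysis outside the spreadsheet. Intervals will be wider. Kaplan-Meier assumes that loss to follow-up is unrelated to implant failure. It does not remove the selection from the 24-month minimum, which should be stated as a limitation.
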